The primary objective of this study will be to test the feasibility and efficacy of a 3 month exercise physiologist consultation program. Specifically, our aims will be to:

- a. Test the feasibility of a 3-month exercise physiologist led program
- b. Measure the effect of an exercise physiologist collaboration and intradialytic exercise on the physical function of HD patients using the 30 second STS test,

handgrip strength test [required for frailty scale], 8-foot TUG test and patient physical activity based off of the Low Physical Activity Questionnaire.

3. Administrative Organization

The study will be administered from Satellite Healthcare, Inc., [name]. The study site will be Satellite Healthcare Milpitas. [name].

4. Study Design

a. Experimental design of the study

Randomized controlled trial (RCT) proof of concept study design

b. Study population

Convenience sample from prevalent HD patients from Satellite Milpitas Hemodialysis center in Northern California.

c. Sample size

n=50 (25 intervention - 25 control)

d. Study Outcomes

Feasibility outcomes

- Adherence calculated as the total number of self-reported exercise sessions attempted by the patient when EP not present divided by the total number of hemodialysis sessions. This information will be collected from the patient at the weekly meeting with the EPs.
- Adverse events defined as any injury, impairment or medical condition that was directly or suspected to be due to performing the prescribed exercise.

Efficacy Outcomes

- Change in physical function as measured by the 30 second sit to stand test (STS), handgrip strength test (HGST) and the 8 foot timed up and go test (TUG). Performed prior to initiation of dialysis at their mid-week dialysis session.

5. Study Procedures

a. Subject selection procedures

The Principal Investigator is responsible for screening subjects for the study, ensuring subjects meet all inclusion criteria.

b. Inclusion criteria

- Age 18 years or greater
- Ability to understand and communicate English
- Diagnosis of ESRD and currently undergoing in-center hemodialysis
- On HD for longer than 6 weeks
- Approved by the Satellite Milpitas Medical Director and/or referring physician

c. Exclusion criteria

- Previous major amputations
- Inability to independently ambulate
- Known to be pregnant

d. Recruitment procedures

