6. For dialysis patients the non-fistula dialysis arm will be used. If both arms have a fistula, then the arm with the inactive fistula will be used. If no fistula is present, then the non-dominant arm will be used.

Reference: (Handgrip Strength Protocol. Tufts University Nutrition Collaborative, 2003)

c. 8 Foot Timed Up and Go

Equipment/set-up

Place a chair (approximately 17 inches in height) against a wall or firm object for safety to prevent it from sliding backwards. Place a cone on the floor exactly 8 ft away (distance measured is from the front edge of the chair to the back edge of the cone). Ensure a minimum of 4 ft of clearance beyond the cone to allow for turning room. A stopwatch is also required.

Starting Position

Patient is seated in the chair with hands on thighs and feet flat on the floor.

Protocol

Patient is instructed that on the signal “go,” they are to rise from the chair (pushing off of thighs or chair is permitted), walk “as quickly as possible” around the cone and return to a seated position in the chair. The participant is told that they will be timed and should therefore walk as quickly as possible but not to run. Following a demonstration, the patient is allowed one practice trial followed by two test trials.

Scoring

The clinician begins the timer when the “go” signal is given (even if the patient has not begun to move) and stops the time at the exact instant that the participant’s buttocks contacts the chair following the walk segment. Note the scores of both test trials to the 1/10th second yet the faster of the two times is recorded on the assessment form for evaluation purposes. Results obtained with this test may be compared to age-related normative values.

Adaptation

Use of an assistive device is permitted if required (remember to mark what type of device the patient used on the evaluation form) yet does not allow for comparison with age related, normative values from the Senior Fitness Test. Be sure to retest the patient using the same device on following visits. Additional trials can be administered without a device or a different type of device if appropriate.

Score > 8.5 seconds is associated with high fall-risk in community-dwelling older adults.

Reference: (Rose, Jones, & Lucchese, 2002)

d. Modified Fried Frailty Index (Frailty = ≥ 3 of the below criteria)

Fried Frailty Index V2.0	
Category	Criteria

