Weight Loss If yes, give one point towards frailty.	Self-reported weight loss ≥ 10 lbs/year based off dry weight. (Yes or No)
Physical endurance/energy If No to #1 OR if every day/every week given as #2 give one point towards frailty.	
 1. Do you feel full of energy? (Yes or No?) 2. During the last month, how often have you rested in bed during the day? (every day, every week, not at all)
Low Physical Activity If no as an answer for very energetic physical activity OR moderately energetic physical activity give one point towards frailty.	Frequency of mildly energetic, moderately energetic and very energetic physical activity using LoPAQ (see attachment e)
Weakness If grip strength is below the 20% cutoff for gender and BMI listed, then give one point towards frailty.	
Hand grip strength in kg, dominant hand, average of 3 measurements
 
Frailty: cutoff point Grip strength lowest 20%
 
Men
 
BMI < 24: < 29 kg BMI 24-26: < 30 kg BMI 26-28: < 30 kg BMI > 28: < 32 kg
 
Women
 
BMI < 23: < 17 kg BMI 23-26: < 17.3 kg BMI 26-29: < 18 kg BMI > 29: < 21 kg

Slow Walking Speed If TUG test takes ≥ 19 seconds then give one point towards frailty.	Timed Up and Go ≥ 19 seconds
If total points towards frailty is ≥ 3 then patient meets criteria for frailty by Fried Frailty Index	

Reference: (Fried et al. Frailty in older adults: evidence for a phenotype. Journal of Gerontology. 2001;56:M146-156);

e. Low Physical Activity Questionnaire

Low Physical Activity Questionnaire (LoPAQ)

1. Please check all of the statements that describe your walking in the last week
 I walked around the neighborhood
I walked _____ times during the week.
I walked for approximately _____ minutes per session.
 I walked for transportation (i.e., to the store, etc.)
I walked _____ times during the week.
I walked approximately _____ minutes per session.
 I walked for the purpose of improving my fitness or for pleasure (above and beyond daily necessities)
I walked _____ times during the week.
I walked approximately _____ minutes per session.
 I did not walk.

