- Make a copy of the updated Exercise Plan form. Provide one to the patient and place one in the Patient Information binder.

3. Weekly visit #12

- Complete the POST-Study Assessment form for both control and intervention patients.
- Complete the Progress Note form.
- Scan the POST-Study Assessment form for all patients and email to [name] at [contact]

4. Reminders

- Report any adverse events (side effects from exercise) to the Center Manager and email [name] at [contact]
- At any point, a patient may choose to leave the study. If this happens, notify the Center Manager [name] and email to [name] at [contact]

Pre and Post Intervention Assessment

Hand Grip Strength Measurements: Using the Handgrip strength dynamometer take the best of three measurements for the non-fistula arm. If both arms have fistulas, use the arm that is not currently being accessed. If no fistula is present, use the non-dominant arm. Chart whether the left or right arm is used for the test. For the post-assessment make sure it is the same hand used in the pre-assessment. Pause 10-20 seconds between each test.

Handgrip Strength		
Test 1:	Test 2:	Test 3:
Average:		Hand Used:

Timed Up and GO (TUG): Record time in seconds for the patient to walk 8 feet in a straight line and return to a seated position. Patient is allowed one practice run. Two are counted. Note the average of the two. Chart if an assistance device such as a walker or cane is needed and note the type of assistance device.

Timed Up and Go (TUG) (seconds)	
Trial #1:	Trial #2:
Average:	Assistance Device:

Sit-to-Stand: Have the patient sit with arms crossed over the chest stand up and sit down as quickly as possible. Record the number of times they can go from sitting to standing in 30 seconds.

Sit-to-Stand (Repetitions/ Time)	
# of repetitions:	Repetitions/Time:

Low Physical Activity Questionnaire: Administer the questionnaire on the following page as instructed. Scan and email back results of this and the above physical function tests to [contact]. [see attachment e]

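### The frailty weakness item is defined on the dominant hand, but the grip test chooses the hand by fistula and records only one, so the weakness point may be misclassified

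*Combined protocol and SAP*

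**What the plan says.** Attachment d, Weakness row, defines the measurement as "Hand grip strength in kg, dominant hand, average of 3 measurements" and scores it thus: "If grip strength is below the 20% cutoff for gender and BMI listed, then give one point towards frailty". The cut-offs run from 29 to 32 kg in men and from 17 to 21 kg in women. The threshold for frailty is: "If total points towards frailty is ≥ 3 then patient meets criteria for frailty by Fried Frailty Index".

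Attachment b, item 6, chooses the hand in another way:

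- Fistula in one arm: "For dialysis patients the non-fistula dialysis arm will be used".
- Fistulas in both arms: "If both arms have a fistula, then the arm with the inactive fistula will be used".
- No fistula: "If no fistula is present, then the non-dominant arm will be used".

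The Pre and Post Intervention Assessment form (attachment i) repeats these rules in its own words. It has one row of three trials and one box for the hand used. It adds: "For the post-assessment make sure it is the same hand used in the pre-assessment".

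Section 2, aim b, says the grip test is needed for the frailty scale, so this single test feeds the weakness item. Section 4d lists change in handgrip strength as an efficacy outcome. Section 6 compares both handgrip and the modified index before and after the intervention.

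**The concern.** For a patient with no fistula, attachment d and attachment b name opposite hands. No separate dominant-hand test is described, so following the plan as written cannot produce the item as defined. This is a rule that contradicts another rule, not a missing detail.

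If the non-dominant hand is weaker, kilogram cut-offs stated for the dominant hand will be missed more often in these patients. Whether a patient gets the point would then depend partly on where the vascular access is. Frailty prevalence and the modified index would be harder to interpret.

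The error may also be impossible to undo later. The form charts left or right, but neither the form nor the data collection plan records handedness. Access is not listed either, unless the dialysis treatment details in section 6 are meant to include it.

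A second conflict can arise during follow-up. The form asks for the same hand at both visits and also for the non-fistula arm. If a fistula is created in the tested arm in between, both cannot be met. Entry requires only "On HD for longer than 6 weeks" and section 5b lists no access criterion, so nothing in the plan rules such patients out.

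**Working it through.** The plan states no frailty prevalence, misclassification rate or effect size on this point, so there is no figure to reproduce. The check is a comparison of the rules, followed by an illustration of size.

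**Step 1. Which hand is tested?**

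| Access at assessment | Hand under attachment b and the form | Hand in attachment d | Mismatch? |
|---|---|---|---|
| Fistula in non-dominant arm only | Dominant | Dominant | No |
| Fistula in dominant arm only | Non-dominant | Dominant | Yes |
| No fistula | Non-dominant | Dominant | Yes, in every such patient |
| Fistulas in both arms | Depends on which is inactive | Dominant | Depends |

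**Step 2. Inputs for the size.** From the plan: n = 50 (section 4c) and cut-offs described as the lowest 20% (attachment d). Assumed, because the plan gives no values:

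- grip is normally distributed, with CV 20-30%;
- the cut-off lies at the 20th percentile of dominant-hand grip in this sample;
- the non-dominant hand is weaker by a fraction r of 0.05 to 0.10, with the same CV;
- a share f of patients is tested on the non-dominant hand.

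**Step 3. Chance of a weakness point in a mismatched patient.** Scale the dominant-hand mean to 1. The cut-off is c = 1 − 0.8416 × CV, and

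p = Φ[(c − (1 − r)) / (CV × (1 − r))].

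- CV 0.20, c = 0.8317. For r = 0.05: (0.8317 − 0.95)/0.19 = −0.623, p = 26.7%. For r = 0.10: (0.8317 − 0.90)/0.18 = −0.380, p = 35.2%.
- CV 0.30, c = 0.7475. For r = 0.05: (0.7475 − 0.95)/0.285 = −0.711, p = 23.9%. For r = 0.10: (0.7475 − 0.90)/0.27 = −0.565, p = 28.6%.

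Against 20%, the rise in a mismatched patient is 3.9 to 15.2 percentage points. With r = 0 it is zero.

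**Step 4. Whole sample.** Share scored weak = 0.20 × (1 − f) + f × p. Excess points = 50 × f × (p − 0.20).

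| Share mismatched, f | Scored weak | Excess points among 50 |
|---|---|---|
| 0 | 20.0% | 0 |
| 0.2 | 20.8-23.0% | 0.4-1.5 |
| 0.5 | 21.9-27.6% | 1.0-3.8 |
| 1 | 23.9-35.2% | 1.9-7.6 |

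The 20% starting level is itself an assumption. If 40% of these patients were below the cut-off on the dominant hand, the same formula with f = 1 would give 3.2 to 10.4 excess points.

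**Step 5. From weakness to frailty.** Frailty needs 3 of 5 points. One extra weakness point changes the status only of a patient who has exactly 2 of the other 4. The number reclassified is therefore a fraction of the figures above, and the plan does not give that fraction.

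**Step 6. A force in the other direction.** Attachments b and d use the average of three trials. The form's instruction takes the highest, beside a box for the average. For three normal trials, the highest exceeds the average by about 0.846 within-person SDs. With an assumed SD of 1-2 kg that is 0.85-1.69 kg upward. A hand difference of 5-10% at cut-offs of 17-32 kg is between 17 × 0.05 = 0.85 kg and 32 × 0.10 = 3.2 kg downward. The ranges overlap, so the net sign is not determined.

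**The case against.** The strongest case is that the conflict in wording may do little harm.

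- A fistula in the non-dominant arm causes no mismatch. If most patients are in that group, the effect is close to zero. This stands: the plan gives no access mix.
- Taking the highest of three trials could offset a weaker hand. This also stands as a limit on direction.
- Both arms follow the same hand rules, so a baseline error should not differ by arm. The same-hand instruction protects the change score unless access changes. Both points stand.
- The modified index is not among the outcomes in section 4d. That is true, but section 6 and the data collection plan include it before and after the intervention, so it will be analysed.
- The same-hand sentence is the specific instruction for the post-assessment and could be read as governing. That reading is possible, but the form states the non-fistula rule as well and makes no exception. The conflict needs a change of access in the tested arm within 12 weeks, and no rate is given.

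None of these points removes the contradiction for patients with no fistula.

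**Conclusion.** The contradiction is established from the text. The weakness item is defined on one hand and, for some patients, collected on the other. In those patients the point may be misclassified, probably upward if the non-dominant hand is weaker. Under the stated assumptions the excess lies between 0 and about 2-8 weakness points among 50 patients, according to the unknown share affected, and fewer patients would change frailty status. The main effect is on frailty classification and the modified index, not on the contrast between arms.

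A reader might infer that frailty is over-scored in this trial. The documents do not support that. They give neither the access mix nor the difference between hands, some patients have no mismatch, the highest-of-three instruction pushes the other way, and a weakness point is not the same as frailty.

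The follow-up conflict is real but contingent. It arises only if access changes in the tested arm, and its frequency cannot be judged from the plan.

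**What to change.** 1. Reconcile attachments b, d and i so that the weakness item and the grip test name the same hand wherever the access rule leaves a choice, that is, in patients with no fistula. State one summary of the three trials in all three places. Rewording attachment d alone would remove the contradiction in the text, but its cut-offs are stated for the dominant hand and their use for the other hand would need justification.
2. Add handedness and access arm to the assessment form. Without handedness, a mismatched item cannot be identified.
3. Where the tested hand is not the dominant one, flag the weakness item and report the modified index with and without it.
4. Compute handgrip change only from the same hand at both visits. If the hand had to change, treat the post value as missing.
5. Have the study team reconcile the same-hand and non-fistula-arm instructions for patients whose access changes. Which arm may be tested is their decision.

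The cost is wording in three attachments, two form fields and one sensitivity analysis. A few post-intervention grip values may be lost.

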- The Satellite Healthcare database will be used to identify all in-center hemodialysis patients at the Satellite Milpitas Dialysis Center
- This list of potential subjects will be approved by the Satellite Milpitas Medical Director who will screen to ensure they meet inclusion criteria.
- The study research associate (RA) and PI ([name]) will meet with the potential screened subjects in the dialysis center at the patient's weekly dialysis sessions
- The RA and PI will describe the study using a one-page information sheet and consent form as approved by the IRB.
- The RA and PI will offer the patient to take the information home and discuss with their relatives and significant others
- The RA and PI will then approach eligible participants again to consent to participate in the study. After consent is obtained, participants will be randomized into two groups using sequentially numbered opaque sealed envelopes.

e. Study Intervention

- 12 exercise physiologist consultations over 12 weeks
- Up to 3 exercise physiologists will implement an individualized resistance exercise program using elastic bands

f. Study Measures and Activities

- Subjects will meet with an exercise physiologist once weekly during one of their usual in-center HD sessions over a 3-month period.
- At the initial visit, the following physical function tests will be performed on the patient by EP: STS, HGST and TUG.
- At subsequent consultations, exercise physiologists will provide exercise plans and collect feedback on the exercises from the patients.
- EPs will tailor exercise routines to the individual patients based on a combined aerobic and resistance exercise program.

Aerobic Exercise

Participants will be asked to commence at a minimum of walking 3 times per week commencing at 20 minutes, and increasing both intensity and time up to 30 minutes x 3 times per week.

Resistance Exercise

Participants will be instructed to initially exercise various upper, core and lower body muscle groups using resistance bands for 1 set of 10 repetitions twice weekly. Intensity and repetitions of exercises will be adapted to participants' abilities throughout the 12 weeks. Warm up and warm down exercises will be included where relevant.

- Weekly progress notes and exercise checklists will be employed to monitor the types of exercises used. (see attachments f-h)
- The estimated duration for the appointments will be 30 minutes

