2. In the past 7 days, did you participate in other activities that would be described as "light" activities? These are activities that make your heart beat a bit faster than usual—you could talk and sing while doing them. Examples would be: light yard or gardening work, bowling, golfing, boating (motor), leisure bicycling, stretching, yoga, chair exercises or light housework such as folding laundry or washing dishes?
 no yes
if yes, I participated in these light activities _____ times during the week for an average of _____ minutes per session.
3. In the past 7 days, did you participate in activities (other than walking) that would be described as "moderate" activities? These activities would make your heart beat faster than usual, and you could talk, but not sing while doing them. Examples of moderate activities would be: aerobics class, swimming (the side stroke or breast stroke), bicycling in the neighborhood, playing badminton or table tennis, softball, downhill skiing or moderate housework such as vacuuming or making beds.
 no yes
if yes, I participated in these moderate activities _____ times during the week for an average of _____ minutes per session.
4. In the past 7 days, did you participate in activities (other than walking) that would be described as "vigorous" activities? These would make your heart beat lots faster, make you breathe heavily, making your talking broken up by large breaths. Examples of vigorous activities would be: jogging or running, playing tennis or racquetball, playing soccer, basketball, cross-country skiing, using stepping machines or other equipment at the gym.
 no yes
if yes, I participated in these vigorous activities _____ times during the week for an average of _____ minutes per session.
5. In the past 7 days, did you do specific exercises for strengthening muscles?
 no yes
if yes, I participated in these strengthening exercises _____ times during the week.
6. In the past 7 days, did you do exercises for stretching your muscles (flexibility exercises)?
 no yes
if yes, I participated in these stretching or flexibility exercises _____ times during the week.
7. In terms of physical activity and walking, was this a typical week for you?
 no yes
8. In the past 7 days, how much time did you spend sitting, watching television, reading or in front of a computer?
_____ hours/day (average)
9. In the past 7 days, did you nap at home during the day?
 no yes
if yes, I napped _____ times.
when you nap, how long do you nap?

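### The low-activity item of the modified frailty index takes no account of walking, which is the trial's own prescribed aerobic exercise

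*Combined protocol and SAP*

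**What the plan says.** The low-activity row of Attachment d names its source as "Frequency of mildly energetic, moderately energetic and very energetic physical activity using LoPAQ (see attachment e". Its scoring instruction is: "If no as an answer for very energetic physical activity OR moderately energetic physical activity give one point towards frailty". It gives no LoPAQ question numbers.

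In Attachment e, activity is spread over several questions:

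- Question 1 covers walking and opens "Please check all of the statements that describe your walking in the last week". It has several tick boxes, with times per week and minutes per session, but no intensity grade.
- Question 2 covers light activity. Its examples include "leisure bicycling, stretching, yoga, chair exercises or light housework".
- Questions 3 and 4 cover moderate and vigorous activity. Both are yes/no, and both ask "did you participate in activities (other than walking) that would be described as" the level concerned.
- Question 5 asks separately about muscle strengthening.

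Section 5f sets the aerobic component at a minimum of "walking 3 times per week commencing at 20 minutes", rising to 30 minutes, and adds resistance-band work. Section 5f also uses the index to assess frailty in both groups at the start. Section 6 compares it before and after the intervention.

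**The concern.** The index is meant to describe frailty at entry and to be compared before and after a programme whose aerobic part is walking. If its activity item cannot register walking, two things follow. At baseline, a regular walker who reports no other moderate or vigorous activity is labelled low-activity. At follow-up, a patient who began with the point and then did all the prescribed walking still carries it, so the walking part of the programme cannot show on that item.

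This differs from the question of whether OR in the rule means either or both. Settling that wording would leave walking outside the item.

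**Working it through.** The plan states no figure here, so the check is of scoring logic.

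**Step 1: which questions feed the item.** The terms moderately and very energetic do not occur in the LoPAQ. Questions 3 (moderate) and 4 (vigorous) are the only yes/no questions that fit. Question 1 has neither an intensity grade nor a yes/no answer. This mapping is an inference, and the rest depends on it.

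**Step 2: points under each reading of OR.**

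| Q3 moderate | Q4 vigorous | Literal rule (point if either is no) | Point only if both are no |
|---|---|---|---|
| no | no | 1 | 1 |
| yes | no | 1 | 0 |
| no | yes | 1 | 0 |
| yes | yes | 0 | 0 |

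**Step 3: patient profiles.**

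| Profile | Q3, Q4 | Literal | Both no |
|---|---|---|---|
| Walks daily, nothing else | no, no | 1 | 1 |
| Prescribed walking, bands reported under Q2 or Q5 | no, no | 1 | 1 |
| Prescribed walking, bands self-rated moderate | yes, no | 1 | 0 |
| Walks, and does housework of the kind listed in Q3 | yes, no | 1 | 0 |

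**Step 4: does walking ever matter?** Treat questions 1 to 5 as yes/no, which gives 2^5 = 32 patterns. The literal rule gives the point in 24 and the both-no reading in 8. Among the 16 patterns with walking, the counts are 12 and 4. Among the 16 without walking they are 24 − 12 = 12 and 8 − 4 = 4. The shares are identical, so the walking answer never changes the item under either reading.

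**Step 5: how often the item could be clear at week 12.** The documents give no response rates. As an illustration only, assume independent yes rates of 10–80% for Q3 and 2–20% for Q4.

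- Literal rule, P(clear) = P(Q3 yes) × P(Q4 yes): from 0.10 × 0.02 = 0.002 to 0.80 × 0.20 = 0.16, or 0.2% to 16%.
- Both-no reading, P(clear) = 1 − P(Q3 no) × P(Q4 no): from 1 − 0.90 × 0.98 = 0.118 to 1 − 0.20 × 0.80 = 0.84, or about 12% to 84%.

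**Step 6: effect on frailty status (cut-off 3 of 5).**

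- One other point: 1 + 1 = 2 with the item, 1 without it. Not frail either way.
- Two other points: 2 + 1 = 3 with the item, 2 without it. Status changes.
- Three other points: 3 + 1 = 4 with the item, 3 without it. Frail either way.

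**The case against.** **The mapping is inferred.** Attachment d never names questions 3 and 4, so a scorer might count walking as moderately energetic. That is a fair limit on the claim. But question 1 offers no intensity from which to do so, and if scorers could differ, that is itself a reason to name the questions.

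**The item is not frozen.** A reader might infer that the programme can hardly ever remove the point, or that the item is close to fixed. The documents do not support this in general. Question 3 is defined by exertion and lists ordinary housework. The protocol does not call the band work chair exercise; its intensity is adapted over the 12 weeks, and it may also be done at home. Under the both-no reading, band work or housework rated moderate clears the point. The stronger claim needs the literal OR. What holds under both readings is narrower: walking does not count.

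**There is no reference standard.** Whether walking ought to count depends on the published index and on the cited comparison of questionnaires, neither of which is available here. So it cannot be said that walkers are wrongly scored against the original instrument. It can be said that the rule labels a regular walker low-activity in a trial that prescribes walking, and that the protocol gives no reason for leaving question 1 out.

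**The consequence is small.** This stands. The efficacy outcomes in Section 4d do not include the index. Frailty is not an eligibility criterion, and no stratification by it is described. Aim b also lists LoPAQ-based activity separately, so the walking data are not lost.

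**Conclusion.** The point holds in limited form. With questions 3 and 4 as the source, the low-activity item ignores walking under either reading of OR, and compliance with the prescribed walking cannot remove the point. Under the literal OR, a single activity rated moderate cannot remove it either; under the both-no reading it can.

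The reach is one of five frailty points, the baseline frailty classification, and the pre/post comparison of the index. A reader might infer that a sizeable share of the 50 patients is misclassified as frail. The documents give neither the proportion who only walk nor the proportion with exactly two other points, so no count can be supported. Low severity.

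**What to change.** **Attachment d.** Name the LoPAQ questions that feed the item. Give the point only when questions 3 and 4 are both no and the walking reported in any box of question 1, as times multiplied by minutes, is below a minimum fixed before any data are seen. A minimum amount is needed so that one short walk does not clear the point. Covering every walking box means that a neighbourhood walker is not missed. This wording also settles the meaning of OR.

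**Section 6.** Keep the five-item score under that rule for the pre/post comparison. Report beside it the four-item score without the activity item (0 to 4, no frailty cut-off applied). Once walking counts, the follow-up item partly records the prescribed exercise itself, which is 3 × 20 = 60 rising to 3 × 30 = 90 minutes a week. The four-item score shows whether any change goes beyond that.

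**Cost.** One row of Attachment d and a sentence or two in Section 6 are reworded, and one analysis is added. No form or visit changes, because question 1 is already collected. The drawback is that the item departs somewhat further from the published index, which the report should state.
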